#### **10.2.2.2 50%, 70%, and 90% responder rates by 3-month interval for observable focal onset seizures over the Evaluation Period**

Summaries and listings for the 50%, 75% and 90% responder rates for observable focal-onset seizures will be provided for the overall Evaluation Period and by 3-month interval. Summaries will also be provided by 3-month interval for number of completers by time interval.

### **10.2.2.3 50%, 70%, and 90% responder rates for focal-onset seizures (all Type I) over the Evaluation Period**

Summaries for the 50%, 75% and 90% responder rates for all Type I seizures will be provided for the overall Evaluation Period and by 3-month interval. Summaries will also be provided by 3-month interval number of completers by time interval.

### **10.2.2.4 Seizure-freedom status for all seizure types by 3-month interval over the Evaluation Period**

The number and percentage of subjects achieving a seizure-free status will be summarized by 3-month interval for each completer cohort. After the study completion, the same summary will be performed for the overall and by 3-month interval for the Evaluation Period.

#### **Change #41**

**The following have been added:**

### **10.2.2.5 Percentage of seizure-free days (for all seizure types) by 3-month interval over the Evaluation Period**

The percentage of seizure-free days and change from baseline in percentage of seizure-free days will be summarized for the overall Evaluation Period and by 3-month interval. Summaries will also be provided by 3-month interval for number of completers by time interval.

### **10.2.2.6 Percentage of reduction in seizure frequency by 3-month interval over the Evaluation Period**

The percentage of reduction in seizure frequency from baseline for observable focal-onset seizures and all Type I seizures will be summarized for the overall Evaluation Period and by 3-month interval. Summaries will also be provided by 3-month interval for each completer cohort.

#### **Change #42**

**The following have been renumbered:**

### **10.2.2.5 Change in the SSG Score**

### **10.2.2.6 Change in the QOLIE-31-P score**

### **10.2.2.7 Change in Hospital Anxiety and Depression Scale (HADS) score**

### **10.2.2.9 Health-related Outcomes and HRU**

### **10.2.2.10 Time to discontinuation**

### **10.2.2.11 Treatment satisfaction**

**Have been renumbered to:**

**10.2.2.7 Change in the SSG Score**

**10.2.2.8 Change in the QOLIE-31-P score**

**10.2.2.9 Change in Hospital Anxiety and Depression Scale (HADS) score**

**10.2.2.10 Health-related Outcomes and HRU**

**10.2.2.11 Time to Discontinuation to Treatment**

**10.2.2.12 Treatment satisfaction**

**Change #43**

**The following has been changed:**

**10.2.2.7 Change in the SSG score**

The numbers and percentages of subjects in each severity category will be summarized descriptively for Entry Visit and at each scheduled assessment visit along with the numbers and percentages of subjects in each of the 7 categories of change (much better through much worse).

Summary will be provided for each scheduled visit and the Last Visit during the Evaluation Period. All data will be listed by subject

**Changed to:**

Data will be listed for each scheduled visit and the Last Visit during the Evaluation Period by subject.

**Change #44**

**The following has been changed:**

**10.2.2.8 Changes in the QOLIE-31-P score**

For each time point, summary statistics will be presented for the change from baseline of the parent study in addition to summaries of the observed values. Only subjects with a non-missing change from baseline will be summarized at each time point.

In addition, all data will be listed by subject for total and subscales.

**Changed to:**

For each time point, the change from baseline of the parent study will be listed by subject for total and subscales.

**Change #45**

**The following has been changed:**

**10.2.2.9 Changes in the Hospital Anxiety and Depression Scale (HADS) score**

The observed scores and changes in the scores will be summarized using descriptive statistics and in addition presented in a subject listing.

**Changed to:**

The observed scores and changes in the scores for depression and anxiety will be presented in a subject listing.

**Change #46**

**The following has been changed:**

**10.2.2.9 Health-related Outcomes and HRU**

Health-related outcomes data and HRU data will be listed for the ES and summarized descriptively for the SS.

- Socio-professional status

Socio-professional status data are collected at Entry Visit and EOS/EDV. Variables include highest level of education, housing status, current professional status, current unemployed status, need for regular assistance due to epilepsy, and ability to drive. The number and percentages of subjects in each category will be summarized for Entry Visit, EOS or the Last Visit during the Evaluation Period.

- Healthcare provider consultations not foreseen by the protocol

The number of health care provider consultations per subject with onset during the Evaluation Period will be summarized as a continuous variable as well as in the following categories: 0, 1, 2, 3, 4, and 5 or more. Additionally, the number and percentage of consultations by type of provider (general practitioner, specialist physician, nurse, and other) will be presented for the Evaluation Period.

- Hospital and ER visits

The number of hospitalization per subject will be summarized as a continuous variable and categorical variable for the Evaluation Period. ER visits will be extracted from the Hospitalization/ER Visit CRF page (if the initial entry point is ER). The number of ER visits will be summarized in the same manner as hospitalizations. Additionally, the number and percentage of subjects with each of the following categories of duration of hospital stay will be summarized: 0 days, 1-5 days, 6-10 days, 11-15 days, and >15 days.

- Caregiver assistance

Caregiver assistance data is collected on the CRFs “Caregiver Assistance” . The number and percentages of subjects having a caregiver will be summarized by visit.

- Concomitant medical procedures

The number of concomitant medical procedures per subject during the Evaluation Period will be summarized using the categories 0, 1, 2, and 3 or more.

**Has been changed to:**

Health-related outcomes data and HRU data will be listed for the SS.

- Socio-professional status

Socio-professional status data are collected at Entry Visit and EOS/EDV. Variables include highest level of education, housing status, current professional status, current unemployed status, need for regular assistance due to epilepsy, and ability to drive.

- Healthcare provider consultations not foreseen by the protocol

Healthcare consultations by type of provider

(general practitioner, specialist physician, nurse, and other) will be listed for each subject during the study.

- Hospital and ER visits

ER visits will be extracted from the

Hospitalization/ER Visit CRF page (if the initial entry point is ER).

- Caregiver assistance

Caregiver assistance data is collected on the CRFs “Caregiver Assistance”.

- Number of school or working days lost

Number of school/working days lost data are collected on the CRFs “School and Workdays Lost”. The number and percentages of subjects who lose school or work days as a result of epilepsy will be listed by visit. The percentage of days lost will be calculated as:

$100 \times (\text{end date of absence} - \text{start date of absence} + 1) / (3 \times 30 + 1)$  for the Entry Visit. If the end date of absence is missing or after Entry Visit date, the end date of absence will be set to Entry Visit; if the start date of absence is missing or prior to Entry Visit-90, the start date of absence will be set to Entry Visit-90.

$100 \times (\text{end date of absence} - \text{start date of absence} + 1) / (\text{visit date of current visit} - \text{visit date of previous visit})$  for the later visits. If the end date of absence is missing or after the current visit date, the end date of absence will be set to the current visit date; if the start date of absence is missing or prior to the previous visit+1, the start date of absence will be set to the previous visit date+1.

If multiple absences are reported at a given visit, the sum of the duration of all absences will be used in the numerator.

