#### 4.1.2 Handling of missing data for adverse events and concomitant medications

For analyses of AEs and concomitant medication usage, a complete date must be established to correctly identify the AE or medication as occurring during treatment or not. In the event of completely missing dates, or if ambiguity or incomplete data makes it impossible to determine whether a medication was concomitant, or an adverse event was treatment emergent, the medication will be considered as concomitant or the adverse event will be considered treatment emergent.

For purposes of imputing missing components of partially-reported start and stop dates for AEs and for medication use, the algorithms listed below will be followed. Start and stop dates of AEs or concomitant medication will be displayed as reported in the subject data listings (i.e., no imputed values will be displayed in data listings). Note that imputed times and dates should not be presented in the patient data listing.

Partial AE and concomitant medication start dates will be imputed as described in the following sections.

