#### **4.1.2.1 Imputation of Partial Start Dates**

- If only the month and year are specified and the month and year of first dose is not the same as the month and year of the start date, then use the 1st of the month
- If only the month and year are specified and the month and year of first dose is the same as the month and year of the start date, then use the date of first dose
- If only the year is specified, and the year of first dose is not the same as the year of the start date, then use the 1st of January of the year of the start date
- If only the year is specified, and the year of first dose is the same as the year of the start date, then use the date of first dose
- If the start date is completely unknown and the stop date is unknown or not prior to the date of first dose, then use the date of first dose.
- If the imputed start date is after the known stop date, set the start date to be the same as the stop date.

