### 10.2.2.10 Health-related Outcomes and HRU

Health-related outcomes data and HRU data will be listed for the SS.

- Socio-professional status

Socio-professional status data are collected at Entry Visit and EOS/EDV. Variables include highest level of education, housing status, current professional status, current unemployed status, need for regular assistance due to epilepsy, and ability to drive.

- Healthcare provider consultations not foreseen by the protocol

Healthcare consultations by type of provider (general practitioner, specialist physician, nurse, and other) will be listed for each subject during the study.

- Hospital and ER visits

ER visits will be extracted from the Hospitalization/ER Visit CRF page (if the initial entry point is ER).

- Caregiver assistance

Caregiver assistance data is collected on the CRFs “Caregiver Assistance”.

- Number of school or working days lost

Number of school/working days lost data are collected on the CRFs “School and Workdays Lost”. The number and percentages of subjects who lose school or work days as a result of epilepsy will be listed by visit. The percentage of days lost will be calculated as:

$100 \times (\text{end date of absence} - \text{start date of absence} + 1) / (3 \times 30 + 1)$  for the Entry Visit. If the end date of absence is missing or after Entry Visit date, the end date of absence will be set to Entry Visit; if the start date of absence is missing or prior to Entry Visit-90, the start date of absence will be set to Entry Visit-90.

$100 \times (\text{end date of absence} - \text{start date of absence} + 1) / (\text{visit date of current visit} - \text{visit date of previous visit})$  for the later visits. If the end date of absence is missing or after the current visit date, the end date of absence will be set to the current visit date; if the start date of absence is missing or prior to the previous visit+1, the start date of absence will be set to the previous visit date+1.

If multiple absences are reported at a given visit, the sum of the duration of all absences will be used in the numerator.

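### The days-lost formula in SAP 10.2.2.10 sets no lower bound on the end date of an absence, so an absence that ended before the previous visit counts as negative days

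*SAP*

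**What the plan says.** SAP 10.2.2.10, under the number of school or working days lost, gives two formulas. The same text stands in SAP 14.1, Change #46, as the replacement wording, so this is current text.

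- **Later visits.** The numerator is end minus start plus 1. The denominator is the current visit date minus the "visit date of previous visit". For the end, which is capped at the day of the visit being assessed: "If the end date of absence is missing or after the current visit date, the end date of absence will be set to" that day. For the start: "if the start date of absence is missing or prior to the previous visit+1, the start date of absence will be set to" the day after the previous visit.
- **Entry Visit.** The numerator has the same form and the denominator is 3 x 30 + 1 = 91. For the end: "If the end date of absence is missing or after Entry Visit date, the end date of absence will be set to Entry Visit". For the start: "if the start date of absence is missing or prior to Entry Visit-90, the start date of absence will be set to Entry Visit-90".
- **Several absences.** "If multiple absences are reported at a given visit, the sum of the duration of all absences will be used in the numerator".

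An absence therefore belongs to the visit at which it is reported. Nothing moves one that was reported late back to the window in which it happened.

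The SAP guards against a start later than its stop in 4.1.2.1: "If the imputed start date is after the known stop date, set the start date to be the same as the stop date". According to 4.1.2, those rules serve for "imputing missing components of partially-reported start and stop dates for AEs and for medication use", so they do not reach absence dates.

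**The concern.** The two resets are meant to cut an absence down to the part that falls between two visits. They do so only if the absence reaches into that window. The start date is pushed forward, but the end date is tested only for being missing or too late, never for being too early. When the whole absence lies before the window, the start overtakes the end and the formula returns a negative count.

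A percentage of days lost below zero is impossible. Because durations are summed within a visit, one such record also lowers the figure for absences that were recorded correctly, and the result may still be positive and look plausible. Days lost is a listed assessment in Protocol 10.5, under the exploratory objective on health-related outcomes and resource use.

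**Working it through.** The plan states no worked figure for this rule, so I applied it as written. The dates are illustrative. Visits on Days 14, 28, 90 and 180 correspond to Weeks 2 and 4 and Months 3 and 6 of the schedule, using the 30-day month of SAP 3.2.5.

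**General result, later visits.** Take an absence that ended on or before the previous visit. The start becomes previous + 1, and the numerator is

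end - (previous + 1) + 1 = end - previous.

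This is 0 if the absence ended on the previous visit date and negative if it ended earlier. It no longer depends on how long the absence lasted.

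**Previous visit Day 90, current visit Day 180, denominator 180 - 90 = 90**

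- Days 100 to 104, inside the window: 104 - 100 + 1 = 5 days, 5/90 = 5.6%. Correct.
- Days 85 to 95, straddling the visit: start moves to 91, 95 - 91 + 1 = 5 days, 5.6%. Correct.
- Days 80 to 90, ending on the visit date: 90 - 91 + 1 = 0. Correct.
- Days 80 to 89: 89 - 91 + 1 = -1 day, -1.1%.
- Days 50 to 54: 54 - 91 + 1 = -36 days, -36/90 = -40%.
- Days 50 to 54 together with a real absence on Days 120 to 129 (10 days): -36 + 10 = -26 days, -28.9%. The real absence alone gives 10/90 = 11.1%.

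**Shorter gap.** Previous visit Day 14, current visit Day 28, absence on Days 5 to 6: 6 - 15 + 1 = -8 days, -8/14 = -57.1%.

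**Entry Visit (EV).** With the start reset to EV - 90, the numerator is end - EV + 91. It is 0 for an absence that ended on EV - 91 and negative for one that ended earlier. An end on EV - 100 gives -9 days, -9/91 = -9.9%.

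**Missing dates, for comparison.** With both dates missing, the rule fills the whole window: (180 - 91 + 1)/90 = 90/90 = 100%. At entry it is 91/91 = 100%.

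**The case against.** The strongest reply is that little hangs on this. SAP 10.2.2.10 says that these data are listed. Amendment 1 of the SAP removed the descriptive summaries of resource use, and no mean, test or model of the percentage is planned. The one aggregate mentioned, the number and percentage of subjects who lose days, does not use this numerator. SAP 3.1 calls for listings of documented as well as calculated data, so the recorded dates should appear beside an odd value. Resource use is recorded at every scheduled visit, so an affected absence must have been missed at an earlier collection. Protocol 11.3.2 and 12.5 foresee cleaning checks and a data evaluation meeting before lock. All of this stands and limits the consequence. It does not repair the formula, because none of those checks is described as covering this case.

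A reader might infer three stronger things that the documents do not support.

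- That the end date is not checked at all, or that any late report goes wrong. The end date is tested for being missing or after the current visit, and absences that reach or straddle the previous visit are handled correctly.
- That the reported percentages are driven by reporting delay. The documents give no frequency of late records, and only affected records, and the sums that contain them, change.
- That 100% for an undated record is an arithmetic error. Filling to the window limits is a stated worst-case convention. The SAP takes the same line elsewhere: adverse events that cannot be dated count as treatment emergent (4.1.2), and missing intensity counts as severe (9.2). A missing end date may also mean that the absence is still going on. The form is not in the documents, so this cannot be settled.

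**Conclusion.** The point holds in a narrow form. Both formulas lack a lower bound on the end date. They return a negative number of days for an absence that ended before the previous visit or, at entry, before EV - 91. The size for one record is the number of days by which it ended before that limit: -36 days (-40%) in the main example, and -26 days instead of +10 when a valid 10-day absence is reported at the same visit.

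This rests on reading the rule literally and on such records reaching the database. An edit check could stop them, but none is described. Nothing in the primary safety or efficacy variables is touched. Severity is low: an exploratory, listed variable with a formula that can give an impossible value.

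**What to change.** In SAP 10.2.2.10, define the contribution of each absence as its overlap with the window:

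- Later visits: max(0, min(end, current visit) - max(start, previous visit + 1) + 1).
- Entry Visit: max(0, min(end, EV) - max(start, EV - 90) + 1).

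The denominators, the summing rule and the filling of missing dates can stay. Records inside or straddling the window do not change. In the main example the late absence contributes 0, and the visit shows 10/90 = 11.1%.

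The cost is two lines of text and the matching lines of the derivation program. The floor does not credit a late-reported absence to the earlier window where it belongs. Doing so would redesign the by-visit listing and is not needed to remove the error. At most, flag records with filled dates as imputed in the listing, so that a 100% resting on no dates can be recognised.

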**Change #47**

**The following has been changed:**

#### **10.2.2.10 Time to discontinuation**

Time to discontinuation is summarized descriptively for FAS overall and by region and parent study.

A Kaplan-Meier figure will be provided for all subjects and by region and parent study.

#### **Has been changed to:**

#### **10.2.2.11 Time to discontinuation**

Kaplan-Meier estimates of the percentage of subjects completing 3, 6, 12, 18, and 24 months of treatment will be provided for the SS. For subjects who discontinued from the study, the event date is set to the date of last dose of PSL and the time to event will be calculated as the date of last dose minus the date of first dose of PSL in EP0093 plus 1. Subjects who completed the study will be censored as of the date of last dose of PSL in EP0093. At a clinical cutoff, subjects who are ongoing will be censored as of the date of last dose of PSL defined for the interim analyses (Section 3.2.2.1).

#### **Change #48**

**The following has been removed:**

#### **10.2.2.12 Treatment satisfaction**

Subscale items will be summarized descriptively for FAS overall and by region.

#### **Change #49**

**The following has been added:**

### **11. COVID-19 impact**

The impact of COVID-19 global pandemic on this study is detailed in section 3.10. COVID-19 impact will be listed by impacted visit, date, impact category, and relationship to COVID-19 (confirmed, suspected, general circumstances around COVID-19 without infection or other) in the ES. Impact of COVID-19 for any reason by country will be tabulated in the ES

#### **Change #50**

**The following has been added:**

### **15. Addendum**

All tables described in the SAP will be repeated for Japan and non-Japan subgroups.

## 15 ADDENDUM

All tables described in the SAP will be repeated for Japan and non-Japan subgroups.

This document cannot be used to support any marketing authorization application and any extensions or variations thereof.

REDACTED COPY

